Treatment cycles will begin on day 1 of each new venetoclax cycle. Patients will receive one cycle every 4-6 weeks; delays of more than 6 weeks may be allowed if determined by the investigator to be in the best interest of the patient, after discussion with the PI and documentation in the patient's medical record.

4.4 Study Duration:

4.4.1. Treatment will continue for 12 total cycles unless discontinuation occurs earlier due to relapse, unacceptable toxicity, or disease progression. Reasons for study treatment discontinuation include:

- clinically significant progressive disease at any time, or
- Possibility of undergoing allogeneic stem cell transplantation
- intercurrent illness that prevents further administration of treatment, or
- unacceptable adverse event(s), or
- patient decision for study withdrawal, or
- general or specific changes in the patient's condition that render the patient unacceptable for further treatment in the judgment of the investigator
- lack of clinical response by 6 cycles of treatment (clinical response as per Section 6.1.1 or 6.1.3 including ORR or hematologic improvement)

Patients may remain on study for the planned 12 cycles of treatment, as long as the patient continues to demonstrate clinical benefit and no excessive toxicity (i.e. no clinically significant study-drug related grade ≥ 3 toxicity).

4.4.2. Dose modifications and interruptions are permitted as necessary for the clinical benefit of the patient. If side effects or toxicity are related to one study drug only; patients may proceed with dose modification and/or discontinuation of that agent and continue treatment with the remaining study agent, if in the investigator's assessment the patient continues to demonstrate clinical benefit and all protocol-specified criteria for continuation of study treatment are met. All dose modifications should be discussed with the PI and clearly documented in the medical record. Treatment may be held as long as clinically necessary for resolution, after discussion with the PI.

For patients with study-drug related clinically significant toxicities, the following dose adjustment rules apply:

- **For Grade 0-2 non-hematological toxicities, no dose reduction is required. For grade 2 toxicities that are persistent and/or intolerable (e.g. stomatitis), patients may have a treatment interruption or dose reduction to the next lower dose level.**

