- **For Grade 3-4 clinically significant non-hematological toxicity, hold until recovery to Grade 0-1, or to baseline if Grade 2 at study entry. Dose should be reduced to -1 dose level, if applicable.**

- Dose reductions beyond those mentioned in Table 1 or different to the doses specified should be discussed with the PI and documentation of the justification recorded in the medical record.

For specific recommendations regarding management of myelosuppression at any time on study, please see guidance in Section 5.6 and 5.7 of protocol.

4.4.3. All patients discontinued from study treatment for any reason other than withdrawal of consent for treatment and follow-up will continue to be assessed for survival. **Survival information (i.e. the date and cause of death) will be collected via telephone calls and/or clinical visits every 3 months (+/- 1 month) for a period of 2 years on any remaining subject that has enrolled on the study.**

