5.2.1. Table of Events

	Screening		Cycle 1			Cycle 2			Add'l Cycles	End of Study (EOS)	
	Cycle Day	-1	1	8	15	22	1	8	15	22	
Study Day	-14 to 0	1	8	15	22	29	36	43	50	-	
Complete history	X		X			X				X	
Physical examination ^a	X		X			X				X	X
TLS prophylaxis initiation		X									
Document all measurable disease (if present)	X										
CBC with differential ^b	X		X	X	X	X	X	X	X	X	
Creatinine, total bilirubin, ALT and/or AST ^b	X		X	X	X	X	X	X	X	X	
TLS Labs (Creatinine, potassium, Calcium, Uric acid, Phosphorus			X ⁱ								
Pregnancy test ^c	X										
Bone marrow biopsy and aspirate ^d	X					Day 21-28				X ^h	X
correlatives on blood ^e			X	X	X	Day 21-28					X
correlatives on bone marrow ^f	X					Day 21-28				X ^f	X

- a) A complete physical examination will be done on day 1 of each cycle (+/- 7 days).
- b) CBC with differential, creatinine, total bilirubin, ALT or AST will be done at least once weekly (+/- 4 days) for the first 2 cycles, then every 2-4 weeks on subsequent cycles.
- c) Pregnancy test either urine or plasma should be done in women of childbearing potential within 72 hours before initiation of protocol therapy.
- d) Bone marrow biopsy and aspiration must be done within 28-days of initiation of therapy; then after cycle 3, cycle 5, every 3 cycles thereafter, and end of study. Cytogenetics and molecular annotation may be used from prior bone marrow analysis (+/- 28 days) if these were not reported on the screening bone marrow.
- e) Correlative studies will be collected on peripheral blood at Day 0 or Day 1 (prior to dosing), day 2, day 5, day 15, and between days 21 to 28 on cycle 1. Subsequently, peripheral blood will be obtained at progression if possible. Window of +/- 1 day during cycle 1, afterwards window will be +/- 7 days.

- f) Correlative studies will be collected on bone marrow at baseline (prior to dosing), on day 28 (+/- 7 days), and at progression.
- g) EOS visits include a physical examination, CBC with differential and platelets and a limited chemistry profile (total bilirubin, serum creatinine, AST or ALT). A bone marrow aspiration may be done if non-response or progressive disease cannot be unequivocally diagnosed from peripheral blood.
- h) At subsequent cycles, bone marrow (aspiration and/or biopsy) will be performed every 3 cycles at the discretion of the treating physician

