5.2.2. Cycle 1 day -1

To mitigate the risk for TLS, subjects must be receiving tumor lysis prophylaxis, including hydration (oral, intravenous) and treatment with a uric acid reducing agent (allopurinol, rasburicase) per institutional guidelines prior to and during the venetoclax ramp-up period of Cycle 1.

5.2.3. Cycle 1 Venetoclax Ramp Up:

Venetoclax will be administered at a dose of 100 mg (or equivalent) on day 1, 200 mg (or equivalent) on day 2, and 400 mg (or equivalent) on day 3-10 of the first cycle or at the RP2D duration.

During cycle 1 venetoclax dosing ramp up, TLS lab monitoring (K+, uric acid, Phosphorus, Calcium and Creatinine) should occur at pre-dose, 6-8 hours post dose, and 24 hours post dose (inpatient AM labs may substitute for the 24 hour post-dose labs if applicable).

No ramp up is required in subsequent cycles.

5.2.4. Treatment Schedule:

All subjects must complete a screening visit, cycle 1 day 1, cycle 1 day 15 visit, day 1 visits for each new cycle, and an end-of-treatment visit.

Patients may remain on study for up to 12 cycles if the patient demonstrates clinical benefit and no excessive toxicity (i.e. no clinically significant non-hematologic study-drug related grade ≥ 3 toxicity). Patients who are experiencing clinical benefit and have not experienced excessive toxicity may be eligible to continue therapy after discussion with the PI and the discussion documented in the patient's medical record.

Bone marrow biopsy and/or aspiration on day 28 (+/- 7 days); if no morphologic evidence of leukemia, venetoclax should be held and bone marrow should be repeated 2 weeks (+/- 7 days) in the absence of count recovery. Bone marrow biopsy and aspiration after cycle 3 and cycle 5; subsequently bone marrow aspirate and/or biopsy, every 3 cycles or as clinically indicated. No repeat bone marrow is necessary if nonresponse or progressive disease can be unequivocally diagnosed from peripheral blood tests.

Cytogenetics should be performed if abnormal pre-therapy, any time a bone marrow exam is performed. Molecular testing depending on the positive tests pre-study (specific mutations, whole genome sequencing) and should be followed any time a bone marrow exam is performed. Omissions will not be considered as deviations.

Multi-parameter flow cytometry for the presence of leukemia associated immunophenotype (minimal residual disease) any time a bone marrow exam is performed. Omissions will not be considered as deviations.

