6.3.1 Leukemia mutation panel

As a standard of care all AML patients at MDACC are evaluated for karyotype and molecular mutation profile using a CLIA-certified next-generation gene sequencing platform. The effects of the combination will be compared not only to historical outcomes in matched groups of patients,

but also at the molecular and cellular level by correlating with karyotype and molecular mutation profile. The Leukemia mutation panel will be performed on the screening BM aspirate and the progression/relapse BM aspirate. An aliquot of DNA will be stored for additional analysis of DNA mutations in responding patients, if these are not identified by the Leukemia mutation panel.

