8.4.2. Efficacy Evaluable Population

All patients who complete at least one post-baseline disease status assessment or who discontinue study medication early due to study drug-related toxicity will be considered evaluable for efficacy. Patients who do not meet the aforementioned requirements will be considered non-evaluable for response and may be replaced.

In addition, we will perform a sensitivity analysis for the efficacy endpoint which will include all patients who have received at least one dose of the study treatment (i.e., those who drop off study early due to any reason will be counted as non-responders).

8.4.3. DLT-evaluable population:

Unless doses are missed in Cycle 1 due to DLT(s), a patient must receive at least 70% of the planned doses of venetoclax and omacetaxine to be considered evaluable for DLT. If a patient received fewer doses/days of treatment in the first cycle of treatment for reasons other than a DLT, the patient will be considered non-evaluable for DLT and replaced.

8.5 Analysis Plan:

Descriptive statistics including plots, mean, median and standard deviations will be used to summarize data. For the primary efficacy analysis, we will estimate the ORR for the combination treatment, along with the Bayesian 95% credible interval. The priors for ORR will be (0.2, 0.8) for AML cohort and (0.15, 0.85) for MDS cohort. Event-free survival (EFS) is defined as the time interval between the date of treatment start and the date of [treatment failure, relapse or death from any cause](#). The Kaplan-Meier method will be used to estimate the probabilities of event-free survival (EFS) and overall survival (OS). Log-rank tests will be used to compare among subgroups of patients in terms of EFS or OS. Similar analyses will be performed for the duration of response. MRD negative status and exploratory biomarkers will be summarized graphically and with descriptive statistics. The association between molecular and cellular markers and overall response and/or resistance will be assessed through logistic regression analyses. Paired t-test or Wilcoxon signed rank test will be used to assess the marker change over time. Safety data will be summarized using frequency and percentage, by category and severity.

The Investigator is responsible for completing an efficacy/safety summary report, and submitting it to the IND Office Medical Affairs and Safety Group, for review and approval

- Phase 1b

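### After treatment stops, section 4.4.3 requires only the date and cause of death, so DOR and EFS have no required relapse date for patients who leave treatment in remission

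*Combined protocol and SAP*

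**What the plan says.** **Endpoints.** Section 1.2.1 lists DOR, EFS and OS as secondary objectives. Section 8.5 runs EFS from treatment start to "treatment failure, relapse or death from any cause", estimated by Kaplan-Meier. For DOR it says only: "Similar analyses will be performed for the duration of response". It gives no censoring rule for either endpoint.

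**On treatment.** Marrows are done at baseline, "then after cycle 3, cycle 5, every 3 cycles thereafter, and end of study" (5.2.1, note d). Section 5.2.4 adds a day-28 marrow and, after cycle 5, further marrows "every 3 cycles or as clinically indicated". Blood counts are weekly for two cycles, then every 2 to 4 weeks (note b). A single end-of-study visit has an examination, counts and limited chemistry; its marrow is listed in note d but optional in note g.

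**Off treatment.** Section 4.4.3 keeps all discontinued patients in survival follow-up unless they withdraw consent: "Survival information (i.e. the date and cause of death) will be collected via telephone calls and/or clinical visits every 3 months", with a window of 1 month either way, for 2 years. It lists no other item.

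**Leaving in remission.** Section 4.4.1 plans 12 cycles. Its reasons for stopping earlier include unacceptable adverse events and "Possibility of undergoing allogeneic stem cell transplantation".

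**Text that bears on relapse.** Note e of 5.2.1: "Subsequently, peripheral blood will be obtained at progression if possible". Note f calls for a correlative marrow at progression. Section 6.3.1: "The Leukemia mutation panel will be performed on the screening BM aspirate and the progression/relapse BM aspirate".

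**The concern.** Both endpoints need a relapse date. A patient who stops because of relapse or progression already has one. A patient who stops without an event passes into a follow-up that, as written, asks only about death.

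The analyst then has two options, and 8.5 does not choose between them. If such patients stay at risk and only deaths are counted, relapse is replaced by a later event, and the late parts of the DOR and EFS curves come out too long. If they are censored at the last assessment, relapse information stops at treatment exit although contact with the patient continues. Patients who leave for transplant or toxicity probably differ in relapse risk from those who stay, so censoring at that point may be informative.

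Durability is part of the rationale. Section 2.2.1 notes that two patients in the earlier low-dose omacetaxine MDS trial had responses of 2 years or longer, both with RUNX1 mutations. For a patient who stops at a nominal cycle 12, the data required here could not document a response of that length.

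**Working it through.** The plan states no figure on this point, so there is none to reproduce. The check is a comparison of the text, then the length of the scheduled window, then a bounded illustration.

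**1. What is required, by period**

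| Item | During cycles | End-of-study visit | After that visit |
|---|---|---|---|
| Blood counts | yes (note b) | yes (note g) | not required |
| Marrow | yes (note d, 5.2.4) | listed in note d, optional in note g | no schedule |
| Relapse status or date | follows from the assessments | follows from the visit | not listed |
| Next therapy, transplant date | – | – | not listed |
| Death: date and cause | yes | yes | yes (4.4.3) |

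Notes e and f and section 6.3.1 describe samples to take when progression occurs. They do not say how an off-treatment relapse is to be found, when to look for it, or that its date must be recorded.

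**2. Nominal length of scheduled relapse follow-up**

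Inputs: 12 cycles (4.4.1) and 4 to 6 weeks per cycle (4.3).

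- 12 × 4 = 48 weeks = 11.0 months
- 12 × 6 = 72 weeks = 16.6 months

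This is not a ceiling. Section 4.3 allows delays beyond 6 weeks, 4.4.2 allows holds for as long as clinically necessary, and 5.2.4 lets patients with benefit continue after discussion with the PI. Transplant and toxicity exits come earlier.

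**3. Worst-case illustration if only deaths were counted off treatment**

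The plan does not state this rule. Assumptions:

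- Time to relapse T among responders is exponential from treatment start, with median m.
- All responders still in remission stop at c = 11.04 or 16.56 months.
- No off-treatment relapse is recorded.
- Survival after relapse, S, is exponential with median 4 or 5.6 months. These are the HMA-failure figures in 2.1.2, used for both arms.
- The documents give no response duration for this combination. The 8 to 10 month median in 2.1.2 is for front-line HMA responders, so 4 and 6 months are also shown.

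Formulas, with T' a fresh draw of T (exponential times have no memory):

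- True month-24 share = 2^(−24/m)
- Recorded month-24 share = 2^(−c/m) × P(T' + S > 24 − c)
- Still in remission at c = 2^(−c/m)

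Example, m = 8, c = 11.04, S median 5.6: 2^(−11.04/8) = 0.384; P(T' + S > 12.96) = 0.615; recorded 0.384 × 0.615 = 0.236; true 0.125; excess 0.111.

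| m (months) | True | Recorded | Excess | In remission at c |
|---|---|---|---|---|
| 4 | 0.016 | 0.036–0.065 | 0.020–0.049 | 0.057–0.148 |
| 6 | 0.063 | 0.106–0.151 | 0.044–0.089 | 0.148–0.279 |
| 8 | 0.125 | 0.184–0.236 | 0.059–0.111 | 0.238–0.384 |
| 10 | 0.189 | 0.257–0.312 | 0.068–0.122 | 0.317–0.465 |

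**4. How many patients**

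The average sample sizes at the design alternatives (scenario 2 of Tables 5 and 7) are 24.8 (AML, response rate 0.40) and 23.0 (MDS, 0.30).

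- Expected responders: 24.8 × 0.4 + 23.0 × 0.3 = 16.8
- In remission at c: 16.8 × 0.057 = 1.0 at the low end, 16.8 × 0.465 = 7.8 at the high end
- Responder share: 16.8 / 47.8 = 0.35
- All-patient EFS excess, if non-responders have had their event by month 24: 0.35 × 0.020 = 0.007 to 0.35 × 0.122 = 0.043

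**5. Against sampling error**

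The standard error of a recorded share p among 16.8 responders is √(p(1 − p)/16.8): 0.045 at p = 0.036 and 0.113 at p = 0.312. Even the worst-case excess is about one standard error at most (0.122 / 0.113 = 1.1).

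**The case against.** The strongest reply has four parts.

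*Relapses will be seen anyway.* Note f asks for a marrow at progression without an if-possible qualifier, and 6.3.1 expects a relapse aspirate. The study is single-center, clinic charts are source documents (7.4), and 4.4.3 allows clinical visits. The case report form is not among the documents and may have a relapse field. This stands in part: some relapses will be dated, and the gap is shown for the protocol text only. But none of these provisions sets a schedule or requires a date, and 5.2.5 allows local care and telemedicine, so capture is likely to be uneven.

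*Treatment may not stop at cycle 12.* Delays and continuation under 5.2.4 lengthen observation. This stands: 11 to 17 months is nominal. It does not help patients who stop or go to transplant.

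*The bias figures rest on a rule that the plan does not contain.* This also stands. A reader might infer that the plan will overstate the month-24 share by up to 12 points. The documents do not support that. Section 8.5 does not say that only deaths count. With censoring at the last assessment this excess does not arise, and for patients who complete the planned cycles such censoring is administrative and shortens follow-up rather than biasing Kaplan-Meier. The illustration also runs from treatment start, so it describes EFS among responders and not DOR. Month 24 is a chosen horizon, because 4.4.3 does not say when its 2 years begin.

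*Nothing is decided on DOR or EFS.* True: they are secondary endpoints with no go/no-go rule. That bears on severity, not on whether the gap exists.

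**Conclusion.** The point holds as a gap in required data. For patients who leave treatment without an event, the protocol neither schedules relapse assessment nor requires a relapse date, and 8.5 does not say how DOR and EFS treat them. Followed as written, the plan either counts deaths alone or ends relapse follow-up at treatment exit, possibly informatively for transplant and toxicity exits.

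The size of any bias cannot be fixed from the documents. Under the assumed response medians of 4 to 10 months, with all remitters stopping at a nominal cycle 12, about 1 to 8 of some 17 responders would be affected. Transplant and toxicity exits are not quantified. The 2 to 12 point excess among responders is a worst case only.

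OS is covered by 4.4.3. The primary ORR, assessed within 3 months or 3 cycles, and the BOIN and BOP2 rules are untouched. This is a cheap improvement, of the nice-to-have kind.

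**What to change.** **Section 4.4.3.** At the 3-monthly contacts already planned, for every patient who left treatment without relapse or progression, also record relapse/progression status and date, next anti-leukemia therapy and its start date, and transplant date. Take these from routine-care results, with no added tests, until relapse, death or the end of the 2 years.

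**Section 8.5.** Censor DOR and EFS at the last known disease-status date for patients without an event. State how transplant and new therapy are handled. Either choice is defensible; one option is not to censor at transplant in the main analysis and to add a sensitivity analysis that does.

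**Cost.** One short amendment and a few CRF fields, with no new visits. Off-treatment relapse dates would depend on routine care, so they would be timed less regularly than on-treatment ones. Dates not collected prospectively may be hard to recover later.

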5.0 STUDY PROCEDURES

5.1 Screening

The following procedures will be performed during screening, staging and workup. These procedures are to be performed within 14 days prior to study drug administration, except as indicated below. The same screening procedures will be performed for both the Phase 1b and Phase 2 study portions.

A signed and dated IRB approved informed consent form must be obtained before any study specific procedures are performed. Procedures that are part of routine care are not considered study specific procedures. All subjects will be screened for eligibility before enrollment. Once the subject has met all inclusion criteria, without meeting any exclusion criteria, they may be enrolled onto the study.

5.2.1. Table of Events

	Screening		Cycle 1			Cycle 2			Add'l Cycles	End of Study (EOS)	
	Cycle Day	-1	1	8	15	22	1	8	15	22	
Study Day	-14 to 0	1	8	15	22	29	36	43	50	-	
Complete history	X		X			X				X	
Physical examination ^a	X		X			X				X	X
TLS prophylaxis initiation		X									
Document all measurable disease (if present)	X										
CBC with differential ^b	X		X	X	X	X	X	X	X	X	
Creatinine, total bilirubin, ALT and/or AST ^b	X		X	X	X	X	X	X	X	X	
TLS Labs (Creatinine, potassium, Calcium, Uric acid, Phosphorus			X ⁱ								
Pregnancy test ^c	X										
Bone marrow biopsy and aspirate ^d	X					Day 21-28				X ^h	X
correlatives on blood ^e			X	X	X	Day 21-28					X
correlatives on bone marrow ^f	X					Day 21-28				X ^f	X

- a) A complete physical examination will be done on day 1 of each cycle (+/- 7 days).
- b) CBC with differential, creatinine, total bilirubin, ALT or AST will be done at least once weekly (+/- 4 days) for the first 2 cycles, then every 2-4 weeks on subsequent cycles.
- c) Pregnancy test either urine or plasma should be done in women of childbearing potential within 72 hours before initiation of protocol therapy.
- d) Bone marrow biopsy and aspiration must be done within 28-days of initiation of therapy; then after cycle 3, cycle 5, every 3 cycles thereafter, and end of study. Cytogenetics and molecular annotation may be used from prior bone marrow analysis (+/- 28 days) if these were not reported on the screening bone marrow.
- e) Correlative studies will be collected on peripheral blood at Day 0 or Day 1 (prior to dosing), day 2, day 5, day 15, and between days 21 to 28 on cycle 1. Subsequently, peripheral blood will be obtained at progression if possible. Window of +/- 1 day during cycle 1, afterwards window will be +/- 7 days.

- f) Correlative studies will be collected on bone marrow at baseline (prior to dosing), on day 28 (+/- 7 days), and at progression.
- g) EOS visits include a physical examination, CBC with differential and platelets and a limited chemistry profile (total bilirubin, serum creatinine, AST or ALT). A bone marrow aspiration may be done if non-response or progressive disease cannot be unequivocally diagnosed from peripheral blood.
- h) At subsequent cycles, bone marrow (aspiration and/or biopsy) will be performed every 3 cycles at the discretion of the treating physician
- i) During cycle 1 venetoclax dosing ramp up, TLS lab monitoring (K+, uric acid, Phosphorus, Calcium and Creatinine) should occur at pre-dose, 6-8 hours post dose, and 24 hours post dose (inpatient AM labs may substitute for the 24 hour post-dose labs if applicable).

Correlative Sample Collection and Specifics:

Samples and Studies	Day 0 (prior to starting Ven and OM)	Day 2 (day after starting daily PO Ven but before OM)	Day 5 (At the end of OM treatment)	Day 15 or 22 (after starting therapy and only if AML is without response or progressing)	Day 28 (End of the first cycle of therapy)
Bone marrow aspirate (BMA) sample for NGS, FCM analysis, and Epigenome/transcriptome/proteome analyses	X			X only if AML is without response or progressing	X
Peripheral blood (PB) and/or BMA (if available) (two 8 ml heparinized green-top tubes) samples for harvesting fresh CD34+ mononuclear cells	X	X		X	X
ATAC-Seq and ChIP-Seq analyses on nuclei to determine accessible chromatin SE/E profile	X		X	X	X
RNA-Seq and QPCR analyses on total RNA to determine mRNA expression for gene-sets and signature profile	X		X	X	X
RPPA/Western on cell lysates to determine protein expression profile	X	X	X	X	X
Flow Cytometry on paraformaldehyde fixed cells	X	X	X	X	X
Confocal microscopy on cytopsued paraformaldehyde-fixed cells	X		X	X	X

